#### 4. Summary and Synopsis

Short title	SAPPHIRE study
Methodology	National, multi-centre prospective observational cohort study collecting only anonymised data
Research sites	NHS hospitals undertaking elective surgery as listed above
Objectives	
 
1. To identify association between the use of perioperative antimicrobial drugs and the incidence of postoperative surgical site infection.
 
2. To identify association between the use of perioperative antimicrobial drugs and other perioperative complications.
 
3. To identify association between antimicrobial allergy labels and perioperative complications.
 

Number of participants	13,720 patients data sets
Inclusion criteria	
Adult patients (aged <math>\geq 18</math> years) undergoing one of the following surgical procedures:
 
 
• Primary hip or knee replacement
 
• Internal fixation of a closed long bone fracture (upper or lower limb)
 
• Colorectal resection
 
• Trans-urethral resection of prostate or bladder tumour
 
• Caesarean section
 
• Hysterectomy (vaginal or abdominal)
 

Exclusion criteria	
 
• Use of antibiotics in the two weeks prior to surgery
 
• Previous participation in the study
 

Statistical methodology and analysis	
Continuous variables will be reported as a mean with standard deviation or median with interquartile range. Multivariable regression analysis will be used to test associations between exposure and outcome measures, adjusting for pre-specified covariates that are plausibly associated with both exposure and outcome. Logistic regression models will be used for binary outcomes and linear regression models for continuous outcomes. The threshold for statistical significance will be 5%. A single final analysis is planned at the end of the study.

Study duration	31 months
----------------	-----------

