The side effects and harms caused by antimicrobial drugs can be substantial, with 1 in 50 surgical patients suffering complications directly attributable to antimicrobial use including acute kidney injury, hearing loss and anaphylaxis. A recent national audit identified antimicrobials as the single commonest cause of life-threatening allergic reactions during surgery. In addition, self-reported antimicrobial allergy can lead to harm from the use of alternative antimicrobial drugs that are less effective and more toxic. Up to 1 in 7 patients carries such a label, although a diagnosis of allergy has rarely been proven through specialist allergy investigation. Previous work has demonstrated that the most common antibiotic allergy is to penicillin, with this label carried by 12% (2624/21,224) of elective surgical patients in the UK. Of such patients, half received second-line antimicrobial drugs and 40% received either no prophylaxis,

or a drug not recommended by local guidelines. Based on these findings, an estimated 100,000 patients every year may be unnecessarily denied penicillin-based antibiotics. Avoidance of penicillin is a recognised cause of harm in a variety of patient groups, associated with increased nosocomial infections, increased wound infections, and higher mortality. Other research has demonstrated increased length of stay for mixed populations of hospital in-patients. The scale of this problem is unknown because there is no system to report antimicrobial use and its associated harms.

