## **7. Study Objectives**

### **7.1. Exposures of interest**

- Number of doses of antimicrobial drugs administered as prophylaxis before, during or after surgery to prevent an infection
- Label of allergy to any drug

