## **9. Statistical Considerations**

We will use a pre-specified statistical analysis plan. The sample size required to detect an association between SSI and dose was calculated using the 'simsam' package in STATA (Version 17.0), which uses simulation. We assumed that dose was a Poisson random variable with mean and variance 2, and that there was a linear relationship between  $\log(p/(1-p))$  and dose, where  $p$  is the risk of SSI. To specify the association we would like power to detect we specified the SSI risk at the mean dose (10%) and the SSI risk at dose 0 (12%), which then determines the coefficients in the linear relationship between  $\log(p/(1-p))$  and dose. To demonstrate an association between dose and SSI risk using logistic regression, with 90% power at the 5% significance level, we require 6000 patients. Also, to demonstrate an association between allergy label (binary exposure) and complications. The incidence of complications in exposed 15% and unexposed 10%, with 80% power at the 5% significance level we require 1372 patients. However, we expect only 10% of the sample to have an allergy label, so the total sample size would need to be 13720. Considering both sample size calculations for our primary and principal secondary outcomes we aim to recruit a total 13720 patients.

The primary analysis will test associations between antimicrobial prophylaxis and surgical site infection. Secondary analyses will examine the association between the type and number of doses of antimicrobial prophylaxis and potential antibiotic-related harms (including allergic reactions, acute kidney injury, diarrhoeal illness within 30 days after surgery), as well as other postoperative infective complications within 30 days after surgery, and mortality at 30 days. In addition, we will examine any associations between the presence of drug allergy labels and SSI, other postoperative infections and antibiotic-related complications. We will report continuous variables as mean with standard deviation or median with interquartile range. We will use multivariable regression analysis to test associations between exposure and outcome measures, adjusting for pre-specified covariates that are plausibly associated with both exposure and outcome. We will use logistic regression models for binary outcomes and linear regression models for continuous outcomes. The threshold for statistical

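### The 10% allergy-label share in section 9 is not reconciled with the protocol's own 12.4% and 1 in 7; the gap is conservative and minor, and it is not the main reason the stated 80% power is wrong

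*Protocol*

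**What the plan says.** Section 9 plans a comparison of complications between patients with and without an allergy label: "The incidence of complications in exposed 15% and unexposed 10%, with 80% power at the 5% significance level we require 1372 patients". It then scales up: "we expect only 10% of the sample to have an allergy label, so the total sample size would need to be 13720". That total exceeds the 6,000 required for the dose analysis, so it becomes the recruitment target, and the synopsis repeats it as "13,720 patients data sets".

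Section 6.1 gives two background figures for label prevalence. One concerns penicillin: "with this label carried by 12% (2624/21,224) of elective surgical patients in the UK". The other concerns self-reported antimicrobial allergy in general: "Up to 1 in 7 patients carries such a label". Section 7.1 defines the exposure more widely than both: "Label of allergy to any drug".

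The protocol gives no source or reason for 10%.

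**The concern.** Penicillin labels are a subset of antimicrobial labels, which are a subset of labels to any drug. Within one population, the prevalence of the section 7.1 exposure therefore cannot be below that of a penicillin label. Yet the planning value is lower than the protocol's own figure for the narrowest of the three.

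The share matters because it enters the step from 1,372 to 13,720. If it is not well founded, the expected number of labelled patients and the precision of the label comparison are not what a reader of section 9 would take them to be.

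**Working it through.** **Inputs.** Section 9: complications 15% (labelled) vs 10% (unlabelled), 80% power, 5% significance, label share 10%, dose requirement 6,000, target 13,720. Section 6.1: 2,624/21,224 = 12.4%, and up to 1/7 = 14.3%. Section 9 does not say whether the test is one- or two-sided; two-sided reproduces its figure, so it is used throughout.

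**Formula.** With n labelled patients, k unlabelled per labelled patient and p̄ = (p1 + k·p0)/(1 + k), the pooled two-proportion test without continuity correction needs

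n = [1.960·√((1 + 1/k)·p̄(1 − p̄)) + 0.8416·√(p1(1 − p1) + p0(1 − p0)/k)]² / (p1 − p0)²

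**Step 1: reproduce the plan.** For k = 1, p̄ = 0.125:

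n = [1.960·√0.21875 + 0.8416·√0.2175]² / 0.0025 = [0.9167 + 0.3925]² / 0.0025 = 685.6, so 686 per group.

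2 × 686 = 1,372 and 1,372/0.10 = 13,720. Both stated figures are matched exactly. The 1,372 therefore counts both groups.

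**Step 2: what the division does.** Dividing the two-group total by the share asks for 1,372 labelled patients and brings in 12,348 unlabelled ones. Power at that size (k = 9, p̄ = 0.105) is

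Φ[(0.05·√1,372 − 1.960·√0.10442) / √0.1375] = Φ[(1.8520 − 0.6333)/0.3708] = Φ(3.29) = 99.95%.

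The stated 80% is already missed at the protocol's own 10%.

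**Step 3: size that gives 80% power at a 10% share.**

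n = [1.960·√0.10442 + 0.8416·√0.1375]² / 0.0025 = [0.6333 + 0.3121]² / 0.0025 = 357.5, so 358 labelled and 358/0.10 = 3,580 in all. 13,720/3,580 = 3.8.

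**Step 4: repeat over the protocol's own shares.** The last column is the difference from a 10% complication rate that 13,720 patients can detect with 80% power.

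| Share | Unequal-group total for 80% power | Labelled at 13,720 | Power at 13,720, 15% vs 10% | Detectable difference |
|---|---|---|---|---|
| 10% | 3,580 | 1,372 | 99.95% | 2.48 points |
| 12% | 3,059 | 1,646 | 99.99% | 2.28 points |
| 12.4% | 2,985 | 1,696 | 99.99% | 2.25 points |
| 14.3% (1 in 7) | 2,653 | 1,960 | above 99.99% | 2.12 points |

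**Step 5: change only the share within the protocol's division.** 1,372/0.12 = 11,433, 1,372/0.1236 = about 11,100, and 1,372 × 7 = 9,604. Against the unequal-group totals these are still about 3.7, 3.7 and 3.6 times too large. Moving the share from 10% to 1 in 7 changes power at 13,720 by less than 0.1 percentage point.

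**The case against.** The strongest answer is that 10% is a cautious planning value for a different mix of patients. The 12.4% comes from elective patients, and 1 in 7 is an upper bound. Section 7.7 also admits fracture fixation, which Appendix A lists under urgent surgery, and caesarean section. A lower share here is possible, and a higher true share could only raise power. This stands: it makes the gap an unexplained difference rather than a contradiction. What it leaves untouched is that the protocol offers no such explanation, while its exposure definition points towards a higher share.

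A reader might also infer more than the protocol supports:

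- **That the evidence rules out 10%.** The 95% interval around 2,624/21,224 (11.9% to 12.8%) excludes 10%, but it covers only sampling error in the cited study. It says nothing about this cohort's case mix.
- **That the low share explains why 13,720 does not match 80% power.** Step 2 shows the mismatch at 10% itself. It comes from dividing a two-group total by the share of one group.
- **That the target should become 11,433 or 9,604.** Those totals inherit the same division and would replace one wrong figure with another.
- **That the label comparison is underpowered.** At every share considered, the power for 15% vs 10% exceeds 99.9%.

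**Conclusion.** The point holds in a limited form. The 10% is below both prevalence figures in section 6.1, although the exposure is broader, and the protocol does not reconcile them. The effect is small: at 13,720 patients, about 1,700 to 1,960 labelled patients rather than 1,372, and a detectable difference of about 2.25 to 2.1 points rather than 2.5.

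The stated 80% power for 13,720 is wrong, but mainly because of the scaling step. Calculated for unequal groups, the label comparison needs about 2,650 to 3,580 patients, so of the two stated requirements the 6,000 for dose would be the larger. No conclusion of the study is endangered, and severity is minor.

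This rests on a two-sided 5% test of two proportions with no allowance for covariate adjustment, clustering by hospital or missing data; section 9 states no such allowance in its calculation. The 6,000 was taken as stated and not re-derived.

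**What to change.** In section 9, either replace the 10% with the protocol's own range of 12.4% to 14.3%, or keep it and give the evidence for a lower share in this case mix.

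Do not restate the total as 1,372 divided by a new share. Say that 1,372 is the total for two equal groups, keep 13,720, and state what it delivers: about 1,372 labelled patients at 10%, 1,696 at 12.4% and 1,960 at 14.3%; power above 99.9% for 15% vs 10%; and a difference from 10% detectable with 80% power of about 2.5, 2.25 and 2.1 points respectively. State the test and that no allowance is made for adjustment, clustering or missing data.

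The cost is one rewritten paragraph. The synopsis figure stays as it is, and no further patients or data are needed.

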### **7.4. Secondary objectives**

To describe any associations between number of doses of antimicrobial prophylaxis or presence of an allergy label and the following:

- Antimicrobial side effects
- Postoperative infections
- Other complications (listed in appendix)
- Mortality at 30 days after surgery

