### **7.5. Secondary outcome measures**

- Number of antimicrobials to treat an infection
- Incidence of antimicrobial side effects within 30 days after surgery:
  - Acute kidney injury of any cause
  - Diarrhoeal illness of any cause

- Hearing loss, tinnitus or vertigo of any cause
- Suspected allergic reaction to antimicrobials
- Suspected allergic reaction to any other drug
- Incidence of postoperative infection within 30 days after surgery
- Incidence of all postoperative complications within 30 days after surgery
- Mortality at 30 days

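### The dose–allergic reaction association cannot be read as a dose effect, because a reaction can itself change the number of doses counted

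*Protocol*

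**What the plan says.** Section 7.1 defines the first exposure as "Number of doses of antimicrobial drugs administered as prophylaxis before, during or after surgery to prevent an infection". It is a count of doses actually given, of any antimicrobial, over the whole perioperative course.

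Section 7.4 sets the secondary aim: "To describe any associations between number of doses of antimicrobial prophylaxis or presence of an allergy label and the following". Antimicrobial side effects head the list that follows. Section 7.5 measures these as "Incidence of antimicrobial side effects within 30 days after surgery" and includes "Suspected allergic reaction to antimicrobials".

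Section 9 repeats the pairing: "Secondary analyses will examine the association between the type and number of doses of antimicrobial prophylaxis and potential antibiotic-related harms (including allergic reactions", followed by acute kidney injury and diarrhoeal illness. The method is fixed there too: "We will use logistic regression models for binary outcomes", "adjusting for pre-specified covariates that are plausibly associated with both exposure and outcome".

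Nowhere does the protocol restrict the count to doses given before the event, use the intended course as exposure, or take the single dose as the unit at risk.

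**The concern.** A dose count is a sound exposure only if the outcome cannot alter it. A suspected reaction can. A patient who reacts to the first dose may get no more and be recorded with one dose and a reaction. A patient who tolerates the drug may be recorded with three doses and no reaction. A regression of reaction on dose count then partly compares people whose course was changed by the reaction with people whose course was not.

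This is reverse causation. The planned adjustment deals with common causes of exposure and outcome, and no set of such covariates removes an effect of the outcome on the exposure.

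Defining the risks of harm is one of the stated aims (section 6.2), and section 6.1 says that limited reporting of harm makes it difficult to balance risk and benefit. A null or distorted dose–allergy result would feed directly into that balance.

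**Working it through.** **The plan's own figures.** The protocol gives no figure for dose against allergic reaction. The only stated figure with dose as exposure is the 6,000 patients for surgical site infection. The slope is [logit(0.10) − logit(0.12)]/2 = (−2.197 + 1.992)/2 = −0.102, an odds ratio (OR) of 0.903 per dose. Simulation (4,000 runs) gives 90.4% power against the stated 90%, so it reproduces. The total also reproduces: 2 × 686 = 1,372, and 1,372/0.10 = 13,720.

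**Inputs.**
- From section 9: N = 13,720, and "We assumed that dose was a Poisson random variable with mean and variance 2". Here that distribution is used for the intended number of doses, M.
- Assumed reaction risks (first dose, each later dose): A = (0.5%, 0), B = (0.5%, 0.25%), C = (0.2%, 0.2%).
- Assumed consequences of a reaction at dose d: the course ends (count = d); half of reactions end it; or every reactor switches to another counted drug (count = the larger of M and d + 1).

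**Formula.** For a rare event, with Poisson(2) counts in patients without it, the logistic slope b satisfies: mean count in reactors = 2e^b. So OR per dose ≈ (mean recorded count in reactors)/2. Needed quantities: P(M≥1) = 1 − e^−2 = 0.8647; P(M=1) = 0.2707; P(M≥2) = 0.5940; E[M] = 2; E[M²] = 6; Σ k·P(M≥k) = E[M(M+1)]/2 = 4.

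**A, first dose only.** Events: 13,720 × 0.8647 × 0.005 = 59.3.
- Intended count: 2/0.8647 = 2.313, OR 1.16
- Course ends: mean 1, OR 0.50 (95% CI 0.39 to 0.64)
- Half end: (1 + 2.313)/2 = 1.657, OR 0.83
- All switch: 2.313 + 0.2707/0.8647 = 2.626, OR 1.31

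**B, lower risk at later doses.** Weight: 0.5 × 0.8647 + 0.25 × (2 − 0.8647) = 0.7162.
- Intended: (0.5 × 2 + 0.25 × 4)/0.7162 = 2.793, OR 1.40
- Course ends: (0.5 × 0.8647 + 0.25 × 3.1353)/0.7162 = 1.698, OR 0.85 (0.73 to 0.99)
- Half end: (1.698 + 2.793)/2 = 2.245, OR 1.12
- All switch: 2.793 + (0.5 × 0.2707 + 0.25 × 0.5940)/0.7162 = 3.189, OR 1.59

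**C, constant risk.** Events: 13,720 × 2 × 0.002 = 54.9.
- Intended: 6/2 = 3, OR 1.50
- Course ends: 4/2 = 2, OR 1.00
- Half end: 2.5, OR 1.25
- All switch: 3 + 0.8647/2 = 3.432, OR 1.72

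A full binomial regression on the expected counts agrees to within 0.01:

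| Reaction risk | Per intended dose | Course ends | Half end | All switch |
|---|---|---|---|---|
| A | 1.16 | 0.50 | 0.83 | 1.31 |
| B | 1.40 | 0.85 | 1.12 | 1.60 |
| C | 1.50 | 1.00 | 1.25 | 1.73 |

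**Zero-dose patients.** These are e^−2 = 13.5% of the cohort and can hardly react to prophylaxis, so they pull the OR up. When the course ends and only patients with at least one dose are analysed, B falls to 0.59, a constant risk (0.5% per dose, simulated) gives 0.80, and A separates completely.

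**Check of the alternative.** Risk per dose administered in C is about 54.8 reactions in 27,385 doses, or 0.20%, which is the value put in. In A the pooled figure is 59.3/27,362 = 0.22%. Splitting by dose order recovers 59.3/11,863 = 0.50% at the first dose and 0 later.

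**The case against.** Four points have force.

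- **The premise is inferred.** No section says that a reaction ends prophylaxis, and the reaction rates are assumed. This stands. A reader might infer that each extra dose will look protective, or at least that the direction of bias is certain. The documents support neither. Under full stopping with a constant risk the harm is masked at 1.00, not reversed. With half stopping it is 1.25. Because section 7.1 counts any antimicrobial given as prophylaxis, a substitute drug adds to the count and can push the OR above the intended-course value.
- **The outcome is wider than the model.** Section 7.5 covers suspected reactions to any antimicrobial within 30 days, including drugs given to treat infection. Reactions after prophylaxis has ended cannot change the count. That dilutes the distortion, but also mixes in events that prophylactic doses did not cause.
- **The statistical analysis plan is not shown.** It may refine the analysis, and section 9 already mentions type of drug and does not fix a linear dose term. But the pairing of administered doses with allergic reaction is stated in the protocol, and categorising the count leaves the reverse causation in place.
- **Acute kidney injury and diarrhoea.** Both are recorded from any cause, and nothing says they alter prophylaxis. With a mean of two doses many onsets would follow the last dose. For these outcomes the problem is a possibility to guard against, not a demonstrated bias.

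**Conclusion.** The point holds in a limited form. The protocol relates a count of administered doses to an outcome that can change that count, and its planned adjustment cannot correct this. The resulting OR per dose depends on what happens after a reaction as well as on the drug.

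Under Poisson(2) doses and the assumed reaction rates, ending the course without replacement biases the OR downward (1.00 against 1.50, or 0.50 against 1.16). Half stopping gives 0.83 to 1.25, still below the intended-course values. Universal switching to a counted drug gives about 1.31 to 1.73, above them. Neither the size nor the sign of the bias can be settled from the documents, so the estimate should not be presented as evidence that more doses are safer or more harmful for allergy. This concerns secondary harm analyses only.

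**What to change.** **Allergic reaction.** In sections 7.4 and 9, do not regress it on total doses received. Report reactions to prophylactic drugs as risk per dose administered: each dose is a unit at risk, up to and including the dose that preceded the reaction. Present this by drug class and dose order among exposed patients. Any dose versus none adds little, since untreated patients can hardly react to prophylaxis.

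**Acute kidney injury and diarrhoea.** Where onset during the course is possible, do not simply cut the count at onset. That shortens it in cases and leaves it whole in non-cases. If the harm did not end the course, this would turn the correct 1.16, 1.40 and 1.50 above into 0.50, 0.85 and 1.00. Use a time-updated exposure, or a common landmark with doses counted up to it and events after it.

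**Data.** If the electronic case report form does not already hold them, record the drug and the dose number or time of the reaction, and the onset date of the other harms. The medical notes are already being reviewed (section 8.4).

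**Cost.** Slightly more data entry and a different exposure scale for these secondary outcomes. A landmark also drops events that occur before it.

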## **10. Ethics**

The Chief Investigators (CI) must ensure that the study is conducted in accordance with the guidelines of the International Conference on Harmonisation, Good Clinical Practice (GCP) and UK legislation. All study documentation will be reviewed and approved by the research ethics committee prior to start of recruitment. Research Ethics Committee (REC), Health Research Authority (HRA) and Sponsor approvals will be in place before patient recruitment commences. The study will be sponsored by QMUL. Additionally, each participating site will ensure that the approval of the relevant trust Research & Development (R&D) department and Ethics Committee is in place and a written confirmation is provided to the Sponsor.

### **10.1. Annual Safety Reporting**

There is no risk of harm to either patients or investigators.

## **11. Public Involvement**

The grant proposal for this study has been designed with the PPI members at The Patient, Carer & Public Involvement and Engagement (PCPIE) group at the Royal College of Anaesthetists. Furthermore, our PPI co-applicant have reviewed the protocol and will continue to advise us for the duration of the study including dissemination of the study results.

